### 5.2.2. QTc Withdrawal Criteria

A subject that meets any of the criteria below will be withdrawn from the study. The same QT correction formula (e.g., QT duration corrected for heart rate by Bazett's formula [QTcB], QT duration corrected for heart rate by Fridericia's formula [QTcF]) should be used to determine inclusion and discontinuation for any individual subject throughout the study.

- [QTcB or QTcF] >500 msec,
- [Change from baseline: QTcB or QTcF >60 msec]
- uncorrected QT >600 msec

If a subject has underlying bundle branch block the following withdrawal criteria should be used instead:

Baseline QTc value (with underlying bundle branch block)	QTc withdrawal criteria
<450 msec	>500 msec
450-480 msec	>530 msec

Withdrawal of subjects is to be based on an average corrected QT interval (QTc) value of triplicate ECGs. If an ECG demonstrates a prolonged QT interval, obtain 2 more ECGs over a brief period of time and then use the averaged QTc values of the 3 ECGs to determine whether the subject should be discontinued from the study.

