### 3. STUDY DESIGN

#### 3.1. Study Schematic

#### 3.2. Study Design Detail

This will be a multicenter, single dose study of intravenous GSK1550188 at a dose of 10 mg/kg in Chinese subjects with SLE.

After the study has been explained to the subjects and they have given full informed consent, the subjects will undergo a medical screen within 30 days prior to the first dose, to determine their eligibility for participation based on the inclusion/exclusion criteria.

After screening, eligible Chinese SLE subjects will be admitted to the study center on Day 0. Each subject will receive the dose on Day 0 after completion of all the pre-dose procedure. The subjects will be kept in the study center up to 24 hours post dosing with subsequent outpatient visits occurring on Days 1, 7, 14, 21, 28, 42, 56, and 84.

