### **3.4. Benefit-Risk Assessment**

Belimumab administered by IV infusion is indicated for reducing disease activity in adult patients with active autoantibody positive SLE who are receiving standard therapy. The benefit/risk profile of belimumab for systemic lupus erythematosus remains favorable. Identified risks include hypersensitivity/infusion reactions and non-opportunistic infections. Potential risks (i.e., based on pharmacology but no association identified to date) include progressive multifocal leukoencephalopathy (PML) and other opportunistic infections; malignancies; immunogenicity; effects on immunizations (including interactions with live vaccine); and psychiatric events including depression and suicidality. The most common AEs reported in the primary safety population of adults with SLE were associated with hypersensitivity/infusion-related reactions, non-opportunistic infections, and symptoms consistent with SLE. The majority of reports of infusion-related and hypersensitivity reactions were non-serious and include symptoms such as nausea, vomiting, diarrhea, chills, fever, rash, urticaria, pruritus, headache, dizziness, and dyspnoea. However, infusion and hypersensitivity reactions can be severe and fatal. Most clinical trial and spontaneous cases of serious hypersensitivity occurred during or within the first hour after the completion of the infusion, although some cases report delayed acute onset (>4 hours but <4 days) or a delayed non-acute onset (4-21 days) hypersensitivity reactions.

Infections have been reported with administration of belimumab and are also associated with both SLE and immunosuppressant medication used to treat SLE. The mechanism of action of belimumab may increase the potential risk for the development of infections. In the phase 2 and 3 clinical trials, there was a slight increase in the overall rate of infections in the belimumab group compared with the placebo group. There was no difference in the rate of serious infections, infections leading to discontinuation, or infections of special interest. Out to 10 years in the Phase 2 and 3 continuation studies, the incidence rate of serious infections has remained stable or declined over time. No association between

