**Table 2 Time and Events Table**

Visit	1	2						3	4	5	6	7	8	9	10	
Day	Screening Day -30 to -1	Day 0						Day 1	Day 7	Day 14	Day 21	Day 28	Day 42	Day 56	Day 84	Discontinuation 
		Pre	0	5m	1h	6h	24h									
Informed consent 	X															
Medical History	X	X														
Demography	X															
Inclusion/Exclusion criteria	X	X 														
Complete physical examination, including Height	X															
Body weight		X														
Vital signs 	X	X	X	X	X	X	X	X	X	X	X	X	X	X	X	X
Record Concomitant Medications	X	X	X	X	X	X	X	X	X	X	X	X	X	X	X	X
Clinical Laboratory test 	X	X 					X			X		X		X	X	X
Spot urine (protein to creatinine ratio)	X															
Urine drug/alcohol screen	X															
HIV, Hepatitis B, C 	X															
Pregnancy test (women) 	X	X 										X			X	X
Chest X ray	X															
12 lead ECG	X	X 					X								X	X
Biological Markers 	X 	X								X		X	X	X	X	
Blood PK sampling		X		X	X	X	X	X	X	X	X	X	X	X	X	

Visit	1	2						3	4	5	6	7	8	9	10	
Day	Screening Day -30 to -1	Day 0						Day 1	Day 7	Day 14	Day 21	Day 28	Day 42	Day 56	Day 84	Discontinuation 
		Pre	0	5m	1h	6h	24h									
AE/SAE Review 	X	X	X	X	X	X	X	X	X	X	X	X	X	X	X	X
Admission to Unit		X 														
Dosing			X													
Discharge							X 									
Outpatient Visit	X							X	X	X	X	X	X	X	X	X

1. Each subject must sign an informed consent form prior to undergoing any Screening assessments.
2. Clinical laboratory test at screening visit will be used for inclusion/exclusion criteria check.
3. Vital signs include temperature, sitting blood pressure and heart rate. Pulse rate could be used to replace heart rate monitoring if subject has regular sinus rhythm.
4. Clinical Laboratory test include hematology, chemistry and urinalysis (including C-reactive protein [CRP] and Erythrocyte Sedimentation Rate on screening). ALT and/or AST elevations of greater than 2.5 x ULN will require additional Hepatitis B assessment, see Section 6.2.1.1. For pre-dose safety lab monitoring including urine pregnancy test and 12 lead ECG, it's recommended to be done on day 0 or within 48 hours prior to day 0 if site logistic management are limited on day 0 for drug dosing and intensive PK sample collection.
5. HIV antibody, Hepatitis B surface antigen, anti-HBc and Hepatitis C antibody.

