#### **6.2.4. 12-Lead ECG**

Measurements of 12-Lead ECG will be taken at screening and at pre-dose, and 24 hours and Day 84 post-dose. The ECG parameters are HR, PR, QRS, QT and QTc.

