#### **6.3. Pharmacokinetics**

Blood samples will be collected for PK at pre-dose, and at 5 minutes, 1, 6 and 24 hours, and Days 1, 7, 14, 21, 28, 42, 56 and 84 post-dose. The actual date and time of sampling will be recorded in the CRF. Serum will be harvested within one hour of blood sample collection. PK samples will be sent to a local bioanalytical laboratory and analyzed using a validated method (details provided in the SPM).

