#### **6.4. Pharmacodynamic/Biomarkers**

Blood samples will be collected at screening and at pre-dose, Days 14, 28, 42, 56 and 84 post-dose. The actual date and time of sampling will be recorded in the CRF. All blood samples will be sent to a central laboratory for analysis (details provided in the SPM). The central laboratory will fax the results to the Investigator and will transmit the results electronically to GlaxoSmithKline.

- B cell subsets (CD20+, CD20+/27+ memory, CD20+/27- naïve, CD20+/69+activated, CD20+/138+ plasmacytoid, CD19+/27BRIGHT/38BRIGHT SLE subset and CD20-/138+ plasma cells).

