##### **7.1.1. Time period for collecting AEs and SAE information**

AEs will be collected from the start of Study Treatment and until the Day 84 or study discontinuation. Medical occurrences that begin prior to the start of study treatment but after obtaining informed consent may be recorded on the Medical History/Current Medical Conditions CRF.

Serious AEs will be recorded from the time the consent form is signed until the follow-up contact. All SAEs will be recorded and reported to GSK within 24 hours.

Investigators are not obligated to actively seek AEs or SAEs in former study participants. However, if the investigator learns of any SAE, including a death, at any time after a subject has been discharged from the study, and he/she considers the event reasonably related to the study treatment or study participation, the investigator would promptly notify GSK.

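### A QTc criterion met at the 24 h ECG stops no dosing in this single-dose study, yet ends most PK sampling and all B-cell sampling for that subject

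*Protocol*

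**What the plan says.** Protocol Section 5.2.2 sets the QTc limits, requires confirmation on the average of triplicate ECGs, and states the consequence: "A subject that meets any of the criteria below will be withdrawn from the study". It does not separate triggers before dosing from triggers after it, and makes no provision for continued follow-up.

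The surrounding schedule is as follows.

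- **Dosing** (Section 3.2): "Each subject will receive the dose on Day 0 after completion of all the pre-dose procedure". There is no second dose, and Section 5.1 gives an infusion of about an hour.
- **ECGs** (Section 6.2.4): after dosing, at "24 hours and Day 84 post-dose" only.
- **PK** (Section 6.3): "Blood samples will be collected for PK at pre-dose, and at 5 minutes, 1, 6 and 24 hours", then on Days 1, 7, 14, 21, 28, 42, 56 and 84. Table 3 places the Day 1 sample at 48 h, so it is separate from the 24 h sample.
- **B cells** (Section 6.4): "Blood samples will be collected at screening and at pre-dose, Days 14, 28, 42, 56 and 84 post-dose". Table 2 limits the screening draw to immunoglobulins and autoantibodies.
- **Discontinuation visit** (Table 2): vital signs, concomitant medication, laboratory tests, pregnancy test, ECG and adverse event review are marked. The row "Blood PK sampling" and the biomarker row are blank in that column.
- **Adverse events** (Section 7.1.1): "AEs will be collected from the start of Study Treatment and until the Day 84 or study discontinuation".

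SAP Section 11.5.1 adds that withdrawn subjects are not replaced and that their available data are kept.

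**The concern.** A withdrawal rule protects a subject mainly by preventing further exposure. Here it can do that only before the infusion. A trigger at Day 84 loses nothing, because that is the last visit. Among the scheduled ECGs, the 24 h ECG is where the rule costs something: exposure has already happened, and the effect of withdrawal is to end observation.

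What ends is the part of the profile that carries the elimination information for the primary objective and every post-dose value of the B-cell endpoint. Routine solicitation of new non-serious adverse events also stops. Section 3.4 of the protocol mentions "delayed non-acute onset (4-21 days) hypersensitivity reactions", so scheduled visits covering part of that period are dropped for a subject who already has a safety finding.

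The liver rule is less abrupt. Under Section 6.2.1 and Appendix 1, withdrawal comes after monitoring is complete, is waived where more safety follow-up is needed, and a PK sample is requested. Section 5.2.2 has none of these features.

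**Working it through.** **1. The plan's own precision figure.** Section 9.2.1 assumes a CV of 20.0% for Cmax and 32.1% for AUC(0-∞) with 12 evaluable subjects. On the log scale, s = √ln(1 + CV²), and the upper 95% bound relative to the point estimate is exp(t(0.975, n−1) × s/√n) − 1.

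- Cmax: s = 0.1980; exp(2.201 × 0.1980/√12) − 1 = 13.4%.
- AUC(0-∞): s = 0.3132; exp(2.201 × 0.3132/√12) − 1 = 22.0%.

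Both match the protocol.

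**2. What one subject loses after a 24 h trigger.**

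| Item | Scheduled post-dose | Up to and including 24 h | Lost |
|---|---|---|---|
| PK samples | 12 | 4 (5 min, 1 h, 6 h, 24 h) | 8 (Days 1, 7, 14, 21, 28, 42, 56, 84) |
| B-cell samples | 5 | 0 | 5 (Days 14, 28, 42, 56, 84) |
| Doses still to give | – | – | 0 |

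The count of 4 assumes that the 24 h PK sample is drawn, which the PK-priority rule in Section 6 supports, and that withdrawal takes effect before the 48 h sample. The eight outpatient visits are replaced by one discontinuation visit, which includes no PK or B-cell sample.

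**3. Visits in the 4–21 day window.** Table 3 times the Day 7, 14 and 21 samples at 192, 360 and 528 h. Dividing by 24 gives 8, 15 and 22 days after dosing. Two visits are nominally inside the window. The third has an allowance of −48 h to +2 h, so it can fall anywhere from 480 h (20 days) to 530 h (about 22.1 days), and is inside only if held at least 24 h early.

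**4. How much of AUC(0-∞) is seen.** Section 1.1.2 gives a bi-exponential decline with a terminal half-life of 19.4 days at 10 mg/kg and a distribution half-life of 1.1–1.8 days. The ratio R of the distribution intercept to the terminal intercept is not given; I assume 0 to 4. With α = ln 2/distribution half-life and β = ln 2/19.4, the fraction observed by T days is

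1 − [R·exp(−αT)/α + exp(−βT)/β] / [R/α + 1/β].

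- T = 1 day: R = 0 gives 1 − 2^(−1/19.4) = 3.5%; the highest value over the range, at R = 4, is 11.5%.
- T = 84 days: R = 0 gives 1 − 2^(−84/19.4) = 95.0%; the highest value, at R = 4, is 96.4%.

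At 24 h, 1/19.4 = 0.05 of a terminal half-life has passed. No credible λz can be fitted, so t1/2, AUC(0-∞), CL and Vz fail with it. AUC(0-t) covers only the first day. Cmax is unaffected.

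**5. Study level.** Same formula for AUC(0-∞), s = 0.3132:

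| n | Upper bound |
|---|---|
| 20 | 15.8% |
| 19 | 16.3% |
| 12 | 22.0% |
| 11 | 23.4% |

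With 20 enrolled to obtain 12 evaluable, 20 − 11 = 9 losses are needed to fall short. The documents give no QTc event rate. At an assumed 0–5% per subject, 20 × 0 = 0 to 20 × 0.05 = 1 subject is expected.

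**The case against.** The strongest reply is that the trigger is unlikely and the study can absorb it. Section 3.4 and Table 1 list no QT risk for belimumab. Inclusion criterion 7 requires QTc below 450 msec (below 480 with bundle branch block), and exclusion criterion 14 removes clinically significant ECG abnormalities that could confound the results. The trigger itself needs a confirmed QTc above 500 msec, a rise above 60 msec or an uncorrected QT above 600 msec (QTc above 500 or 530 msec, by baseline, with bundle branch block). The study is descriptive, and the planned enrolment already allows eight non-evaluable subjects. Releasing a subject with a marked QTc finding from research procedures is also a defensible conservative choice. All of this stands, and it is why the point is rated low. It shows that the event is rare, not that ending follow-up helps a subject who has already been dosed.

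A reader might infer that the withdrawn subject is left without safety oversight. The documents do not support that. Recorded adverse events are followed to resolution even after withdrawal (Section 7.1.11), and the QTc finding is itself one if judged clinically significant (Section 7.1.4). Related serious events learned of later are reported (Section 7.1.1), and pregnancy reporting runs to 16 weeks (Section 7.2). Section 5.5 has subjects told about reaction symptoms and the need to seek care at once, and Section 3.4 says most serious hypersensitivity arises during the infusion or within an hour of its end. What is lost is solicited reporting of new non-serious events.

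A reader might also count three visits inside the 4–21 day window from the day labels. Table 3 supports two.

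SAP Section 8.1.3 allows population PK modelling if the data permit. It could use the truncated profile, but a 24 h profile says little about elimination and the modelling is not certain to be done.

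**Conclusion.** The point holds for the individual subject. A criterion confirmed at 24 h leaves 4 of 12 post-dose PK samples and 0 of 5 post-dose B-cell samples, five of the seven primary PK parameters cannot be credibly estimated, and visits nominally at 8 and 15 days after dosing are dropped from the delayed-hypersensitivity window. Nothing elsewhere in the documents restores the PK or B-cell samples.

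It would be tempting to read this as a threat to the study's result or its evaluable number. The figures do not support that: one loss moves the AUC(0-∞) bound by 0.5 percentage points at 20 subjects or 1.4 at 12, and the number affected may be zero. The coverage range rests on the assumed intercept ratio, and the 0–1 expected subjects on the assumed event rate. The sample counts rest on neither. This is an optional improvement of low severity.

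**What to change.** Keep the thresholds and the triplicate confirmation. Add one sentence to Section 5.2.2: a subject who meets a criterion after dosing is not withdrawn from follow-up but, with consent and subject to clinical judgement, continues the scheduled PK, B-cell, ECG, laboratory and adverse event assessments to Day 84.

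No new wording is needed for triggers before dosing, since withdrawal at that point already prevents the dose, and a bar on further study drug would add nothing in a single-dose study.

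The cost is a short amendment; the visits and samples are already scheduled. The downside is continued study visits for a subject with a QTc finding, which the consent and clinical-judgement conditions are there to manage.

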### 5.3. Blinding

This will be an open label study.

### 5.4. Packaging and Labeling

The contents of the label will be in accordance with all applicable regulatory requirements. Label on each vial and box includes study protocol number, name of investigational drug, serial number, storage condition and study sponsor.

### 5.5. Preparation/Handling/Storage/Accountability

The 400 mg single use vial of active IP will be reconstituted with 4.8 MI SWFI, to yield a final concentration of 80 mg/ML of GSK1550188. After reconstitution the material is stable for up to 8 hours at 2-8°C, or at room temperature.

All IPs must be stored in a secure area with access limited to the investigator and authorized site staff and under physical conditions that are consistent with IP-specific requirements. All treatment packs will be stored refrigerated at 2-8°C. Maintenance of a temperature log (manual or automated) is required. Only authorized site staff may supply or administer IP. IP must be dispensed or administered according to procedures described

herein. Only subjects enrolled in the study may receive IP, in accordance with all applicable regulatory requirements.

The investigator, institution, or the head of the medical institution (where applicable) is responsible for study treatment accountability, reconciliation, and record maintenance. The investigator or the head of the medical institution (where applicable), or designated site staff (e.g., storage manager, where applicable) must maintain study treatment accountability records throughout the course of the study. The responsible person(s) will document the amount of study treatment received from and returned to GSK and the amount supplied and/or administered to and/or returned by subjects. Discrepancies are to be reconciled or resolved. Procedures for final disposition of unused study treatment are listed in the study procedures manual (SPM).

In the post-marketing setting, delayed onset of symptoms of acute hypersensitivity reactions has been observed. Subjects should remain under clinical supervision for 3 hours after completion of the infusion. Should symptoms of acute hypersensitivity occur, an extended period of monitoring may be appropriate, based on clinical judgement. Otherwise, subjects will be monitored during and after each infusion according to study sites' guidelines or standard operating procedure for IV infusions. This may include, but is not limited to, monitoring vital signs and observing for any untoward reactions.

Subjects should be made aware of the potential risk, the signs and symptoms of such reactions, and the importance of immediately seeking medical attention. Trained rescue personnel and rescue medications/equipment should be available for the infusion.

For subjects who have previously received IVIG or subjects with a history of allergies (allergic responses to food, drugs, insects, or a history of urticaria), diphenhydramine (12.5 to 50 mg based on clinical judgment) or equivalent and paracetamol (acetaminophen), should be administered prophylactically, prior to dosing. Antihistamine H2-receptor antagonists (e.g., ranitidine) are also permitted. Sites are encouraged to follow their standard practices to manage any untoward infusion reactions noted during the infusion period.

### **5.5.1. Occupational Safety**

Under normal conditions of handling and administration, the IP is not expected to pose significant safety risks to site staff.

Adequate precautions must be taken to avoid direct eye or skin contact and to avoid the generation of aerosols or mists. The monitor must be notified of any unintentional occupational exposure.

The Procedures for Handling Ips describing the occupational hazards and recommended handling precautions will be provided to site staff.

## **5.6. Assessment of Compliance**

When the individual dose for a subject is prepared from a bulk supply, the preparation of the dose will be confirmed by a second member of the study site staff.

When subjects are dosed at the study site, they will receive study treatment directly from the investigator or designee, under medical supervision. The date and time of each dose administered in the clinic will be recorded in the source documents. The dose of study treatment and study participant identification will be confirmed at the time of dosing by a member of the study site staff other than the person administering the study treatment.

## **5.7. Concomitant Medications and Non-Drug Therapies**

### **5.7.1. Permitted Medications**

Use of the medications may be continued if they have been used before the screening visit. Their dosage and administration, however, should be unchanged during the screening period.

Once the subject is enrolled and receives belimumab on Day 0, the investigator may adjust concurrent medications (add, eliminate, change dose level/frequency) as clinically required. For subjects with a history of allergies, allergic responses to food, drugs or insects, or a history of urticaria, antihistamine and acetaminophen may be administered prophylactically.

All prescription and over-the-counter medications (including herbal medicines) that have been taken within 60 days prior to the first infusion of study treatment and all concomitant medications taken during the study will be recorded in the CRF.

### **5.7.2. Prohibited Medications and Non-Drug Therapies**

**The following medications and therapies are prohibited:**

#### **From 12 months prior to Day 0:**

- Biologic investigational and non-investigational agent

#### **From 6 months prior to Day 0:**

- Hemodialysis
- Intravenous cyclophosphamide (Cytosan)
- High-dose prednisone (>60 mg/day)
- IVIG
- Plasmapheresis

**From 2 months prior to Day 0:**

- Non-biologic investigational agent.
- Corticosteroids (prednisone or prednisone equivalent, >40 mg/day)
- Parenteral antibiotics

**From 30 days prior to Day 0**

- Live vaccine

**During the study period:**

- Other investigational agents (biologic or non-biologic). Investigational applies to any drug not approved for sale in the country in which it is being used.
- Co-enrolment into another study of an investigational agent or non-drug therapy that may interfere with the conduct of this protocol.
- Anti- tumour necrosis factor (TNF) or anti-interleukin-6 (IL-6) therapy (e.g., adalimumab, etanercept, infliximab).
- Other biologics (e.g., rituximab, abatacept, interleukin-1 receptor antagonist [anakinra]).
- Intravenous immunoglobulin (IVIG).
- IV cyclophosphamide.
- Plasmapheresis, leukapheresis.
- Live vaccine.

